## **Procedures and design**

### ***Pretreatment***

Consent: Subjects who present requesting treatment and meet the above criteria will be asked to attend a baseline interview, at which time written informed consent will be obtained by a

APPROVED BY THE YALE UNIVERSITY IRB 10/11/2018 VALID THROUGH 10/13/2019  
research assistant prior to further evaluation. Given that the study involves the potential use of naltrexone, a wallet card indicating the study number, contact information and the subject's study identification number will be prepared for subjects to carry in the event of an emergency.

Collection of Patient Locator Information: Retention and tracking strategies developed in the NIAAA Project Match and previously used by our group will help minimize participant attrition [122, 124]. [name] connections with the clinics from which patients will be recruited will enhance the ability to follow patients and keep them engaged in the study. Locator information on up to 5 individuals will be obtained on all study subjects at enrollment. To set up and confirm appointments, research assistants will notify each subject by phone, including through electronic text messaging, and/or mail before subjects are expected to return for their next assessment. Approximately 1-2 weeks prior to the monthly and quarterly interviews a registered confirmation letter will be mailed to the patient. If after three attempts by telephone the patient is not contacted, contact with the other 4 locators will be initiated, and if unsuccessful a registered letter will be sent to the patient. If at this point the research assistant can not contact the patient, he/she will notify the project director who will try all the locators as well as investigate the support systems noted on the index visit. Subjects will also receive compensation for completing assessments during treatment and at the 9-month and 12-month follow-up.

Pretreatment Assessment: The baseline interview will include evaluations for alcohol, drug, and psychiatric disorders, a physical examination, blood work, urine sample and pregnancy test for women.

Randomization: Eligible participants will be randomly assigned to VIVITROL + MM/MC or placebo + MM/MC by the investigational pharmacist. All staff, other than this individual and the study biostatistician(s), will be blind to treatment allocation. Subjects will be assigned to one of the two conditions using stratified randomization. There will be 6 strata: (a) participating clinic (3) and (b) alcohol abuse/dependence (Yes/No; 2) in the randomization scheme.

### ***Treatment***

#### Medication: VIVITROL versus placebo:

Medication: VIVITROL versus placebo: Participants will receive either active VIVITROL or placebo throughout the 24-week treatment period; they will be told that they have a 50% chance of receiving the active drug. Those assigned to the VIVITROL arm will receive monthly extended release VIVITROL doses at 380mg (4 mL), administered as an intramuscular gluteal injection at 4-week intervals. Consistent with prior studies [60], we will encourage patients to be abstinent from alcohol use for four days or more prior to receiving the dose of extended release VIVITROL. We chose the 380mg dose because it was found in a recent randomized trial to be more efficacious than a 190mg dose with no significant differences in side effects or rates of hepatotoxicity. For the placebo arm of the study, patients will be dosed in a similar manner receiving 4 mL injections of placebo at 4-week intervals. All active and placebo doses will be administered by the study nurse.

Counseling Intervention: Our compound counseling intervention will consist of two efficacious, manualized behavioral treatments intended to augment VIVITROL's effects: Medical Management (MM) and Medication Coaching (MC). MM is a manual-guided supportive counseling therapy with demonstrated effectiveness (see the COMBINE Study [10], Appendix B). This treatment incorporates the clinical skills and advice used by primary

APPROVED BY THE YALE UNIVERSITY IRB 10/11/2018 VALID THROUGH 10/13/2019  
care practitioners supplemented with referrals for all patients to Alcoholics Anonymous. The initial MM visit will consist of: discussion of medical concerns, information on VIVITROL, assessment of medication compliance, provision of written educational materials on alcohol problems and treatment, and a question/answer period. The core elements covered at each follow-up MM visit are: 1) Medical status, medication safety, medication adherence, 2) Drinking status, and 3) Troubleshooting based on patients' drinking and medication adherence status. Each follow-up visit will include approximately 10-15 minutes of MM counseling.

Medication Coaching (MC) is a counseling strategy focusing on HAART medication adherence in substance abusing populations [11] (Appendix C), an early version of which we piloted in our recent study examining the use of buprenorphine for the treatment of opioid dependence in HIV-infected patients [100, 101]. This counseling uses ten strategies to increase medication adherence during the intervention and promote long-term maintenance: 1) assessing adherence, 2) designing an individual adherence management plan, 3) coordinating with medical care, 4) collaborating with other team members (e.g., substance abuse counseling), 5) developing a medication routine, 6) addressing barriers, 7) providing feedback on health outcomes, 8) maintaining adherence, 9) reducing HIV progression, and 10) promoting continued adherence and assessing goals. Each follow-up visit will include approximately 10-15 minutes of MC counseling.

Both treatments will be provided during 8 counseling sessions at week 0, 2, 4, 6, 8, 12, 16 and 20. We have added two booster sessions at weeks 20 and 24 in order to target multiple risk behaviors simultaneously and also to provide an opportunity to provide health feedback at 6-months post-enrollment. Each of these visits will be guided by a structured initial visit or progress note.

The treatments will be delivered consecutively within each session by a trained primary care practitioner (e.g., nurse), with the exception of overlapping content that has been integrated to increase treatment efficiency. For example, we have selected the more detailed adherence assessment from the MM and adapted it to include antiretroviral medications, followed by the more comprehensive multimodal strategies for increasing medication adherence (e.g., cueing strategies, building social support for adherence) taken from the MC. We have also adapted the MM by tailoring the medical evaluation and medical feedback components to include medical comorbidities associated with HIV, further caveats about liver disease, and the adverse medical consequences of using alcohol when HIV-infected. Finally, we have incorporated brief strategies for addressing possible concerns about stigma when trying to engage clients in support groups for abstinence.

Adherence to the MM and MC manuals, as well as competence/performance of the practitioners, will be assessed throughout the study during weekly supervision and through ratings of audiotapes evaluated by blinded trained raters, using rating forms to assess time spent with the patient, content material reviewed, and proficiency of the provider at each session.

**Study Period:** The study period will be 24 weeks. This length was chosen because the largest study of extended release VIVITROL conducted to date followed outcomes over 24 weeks of active treatment [61]. In addition, this period will give adequate time for us to detect differences in adherence, biologic markers (e.g. CD4 lymphocyte counts, HIV RNA, and alcohol and HAART hepatotoxicity) that may emerge. Given that there is some evidence VIVITROL treatment effects do not persist at follow-up after treatment [10], we are planning to conduct follow-up assessments at 9 months and 12 months.

***Treatment setting*****Yale-New Haven Hospital Nathan Smith Clinic (NSC)**

The NSC is located within the Yale-New Haven Hospital Medical Center and provides care for over 775 patients with HIV/AIDS, 40% of whom are women. In a review of clinical data from the electronic medical record maintained on all patients at the NSC over the past two years, the prevalence of alcohol abuse and dependence in patients receiving their care in the NSC was 139/775 or 18%. We suspect that this is an under-estimation of the actual prevalence. Of note, [name] has been an HIV provider in the NSC for the past 12 years and has coordinated addiction treatment studies there for the past 7 years.

**Assessments*****Overview***

We plan to assess a range of pretreatment measures at the baseline assessment to ensure that participants meet eligibility criteria and that important baseline and predictor variables are assessed (see Table 1 for Summary of Study Assessments). Using validated instruments during treatment and at end-of-treatment, we will be able to examine the differential impact of VIVITROL on a range of measures, including medication adherence and standard assessments of alcohol consumption used across NIAAA studies of alcohol treatment. The primary study outcome is adherence to HAART medications. Secondary study outcomes include: 1) Frequency of heavy drinking; 2) HIV viral mutations; 3) Change in biological markers (CD4 lymphocyte counts and HIV RNA); 4) Alcohol-HAART hepatotoxicity; and 5) Sexual risk behaviors.

***Baseline and in-treatment assessments***

Prior to entrance into the study each patient will undergo a medical history, physical and laboratory assessments (Complete blood count (CBC), chemistry panel, and viral hepatitis serologies). A urine pregnancy test will be performed at baseline and each month thereafter and must be negative throughout the study. The research assistant will collect demographic data including items such as marital status, highest level of education completed, employment, substance use history, duration of HIV disease, and a detailed HAART medication history. Charts will be extracted to collect information including medical co-morbidities, prior CD4 lymphocyte cell counts and HIV RNA levels, HAART medication history, historical genotypic information from prior HIV drug resistance testing, and patient satisfaction data.

**HAART medication adherence**, with the goal of determining the proportion of patients achieving 95% or greater HAART adherence, will be measured using pharmacy fill/refill data using the medication possession ratio defined as the total days supply/refill interval. Information needed to calculate the medication possession ratio is readily available in the patient's pharmacy data. With subject written consent, we will call the pharmacy designated by the subject to determine refill dates and days supply of medication. In addition, self-reported HAART adherence will be collected using the AIDS Clinical Trials Group (ACTG) assessment [128]. Patients will be asked how often they took each of their medications during the preceding month. We will also be conducting the Morisky 4-item adherence scale, a brief "persistence" measurement for medication persistence, and a single item visual analog scale for adherence. We will use a valid adjustment strategy [129] to resolve discrepancies between the various methods of assessing HAART adherence. The use of electronic drug monitoring in the form of medication event monitoring system (MEMS) caps for measuring HAART adherence was considered as it offers the best correlation with virologic outcomes [130]. However, several documented disadvantages such as expense, lack of feasibility for most

APPROVED BY THE YALE UNIVERSITY IRB 10/11/2018 VALID THROUGH 10/13/2019  
clinical settings, and the likelihood of underestimation of adherence due to patients' "pocket dosing" their medication or removing more than one dose for each bottle opening, lead us to choose the other three methods in order to measure adherence [130].

We anticipate that a number of HIV-infected patients with heavy drinking may not be prescribed HAART medications due to their providers' concerns about poor medication adherence. While such patients do not meet the second eligibility criterion, we will encourage interested patients to discuss the possibility of resuming HAART with their HIV providers, such that they could be considered for enrollment at a later date. In addition, in an effort to include this target sub-population without mandating the usual 90 days of HAART-adherence data, we will determine their baseline adherence after 30 days; patients will be invited to present for an eligibility assessment one month after their first HAART prescription. We will use a simple 30-day pill count to calculate their baseline adherence.

**The Morisky scale** is a commonly used, validated, 4-item self-reported adherence measure that has been shown to be predictive of medication adherence. It includes two items that measure intentional medication non-adherence.

**Alcohol Use** will be assessed using the Time-Line Follow Back Interview (TLFB) [131] which will obtain the quantity/frequency of alcohol consumed for each day in the past month (baseline) and since the prior visit. TLFB has good test-retest reliability and good validity [131]. In addition, in order to better determine the "category" of drinking behavior of a subject at baseline, we will use the Alcohol Use Disorders Identification Test (AUDIT) [26], a valid instrument for categorizing alcohol consumption.

**The Obsessive-Compulsive Drinking Scale (OCDS)** is a 14-item, self-administered questionnaire for characterizing and quantifying the obsessive and compulsive cognitive aspects of craving and heavy (alcoholic) drinking, such as drinking-related thought, urges to drink, and the ability to resist those thoughts and urges.

**Phosphatidyl ethanol (PEth)**, a phospholipid formed only in the presence of alcohol, has shown 95-100% sensitivity and 100% specificity to detect heavy drinking over a period of 2-3 weeks in several studies of dependent patients and abstainers in Europe. The detection of PEth appears to be dose-dependent. The threshold for PEth is around 1000 grams over 2-3 weeks with a mean daily intake of 50 grams (4.2 standard drinks). The identification of serum PEth will be performed by liquid chromatography-tandem mass spectrometry (LC-MS-MS) as previously described.

**Rates of viral mutations**, according to International AIDS Society guidelines [132], will be determined by collecting plasma and conducting standard HIV drug resistance testing. We will also collect historical genotypic information through chart review. Our team has extensive experience in DNA sequencing techniques and has used these methods in HIV transmission risk studies [34, 133, 134]. For patients with a detectable viral load (>400 HIV RNA copies/mL) we will conduct standard HIV drug resistance testing [34, 133, 134] at baseline and follow up. Standard DNA sequencing will be performed using a consensus population sequencing of the HIV-1 *pol* gene [135]. In addition, a sample from each monthly blood draw will be archived. Ultimately these samples will be processed in a batched fashion and a second aliquot of HIV RNA from the patient sample will be screened for high and low abundance resistant variants (to ~1% levels) by ultra-deep sequencing techniques [33, 38, 136].

**CD4 lymphocyte counts and HIV RNA levels** will be checked at baseline and monthly.

**Potential alcohol/HAART interactions** resulting in hepatotoxicity will be evaluated with monthly liver function tests including AST, ALT and gamma-glutamyl transpeptidase (GGT). We will also collect monthly platelet counts to calculate an AST to platelet ratio index (APRI) and FIB-4. APRI and FIB-4 represent commonly utilized fibrosis indices which provide non-invasive assessments using readily available clinical markers. The AST-platelet ratio index

(APRI) index 
$$\left( \frac{AST * ULN * 100}{platelets} \right)$$
 (calculated as  $[AST \times ULN \times 100] / [\text{platelet count (10}^9/\text{L})]$ )

and FIB-4 score 
$$\left( \frac{age * AST}{ALT * \sqrt{platelets}} \right)$$
 (calculated as  $[age \times AST] / [ALT \times \sqrt{platelets}]$ )

scores, represent validated surrogate fibrosis indices used to distinguish no or minimal liver fibrosis from advanced fibrosis and cirrhosis. Based on validation studies in a spectrum of cohorts with chronic HCV and HIV infection, scores of  $FIB-4 > 3.25$  were used to designate advanced fibrosis or cirrhosis. Scores of  $FIB-4 < 1.45$  were used to designate the absence of significant fibrosis. Monthly blood work will also include creatinine and hemoglobin levels to incorporate into the VACs Index, a scoring system that assesses both HIV-related and - unrelated morbidity/mortality.

**Sexual risk behaviors** will be measured using a modified assessment incorporating specific questions from the High Risk Behavior Survey (HRBS) [137], a validated instrument that measures sexual risk (non-condom use, multiple partners) behaviors that have been associated in previous studies with HIV serostatus and seroconversion.

**Side effects/adverse experiences** will be collected at each visit using the Systematic Assessment for Treatment Emergent Effects (SAFTEE) [102], a validated measure of side effects in clinical trials.

**The alcohol and drug use disorders** section of the Structured Clinical Interview for DSM-IV-TR Axis I Disorders (SCID-I/P) [138] will assess for past or present alcohol use disorders [139] at baseline.

**Lifetime and current DSM-IV-TR Axis I and II psychiatric disorders** will be assessed using the Structured Clinical Interview for DSM-IV (SCID) [138].

**Blood Alcohol Concentration** (breathalyzer) will be obtained at baseline and at each visit. We will use this data to monitor patients and identify those in whom self-report would be suspect (e.g. BAC  $> 0.4$ ).

**The Addiction Severity Index 5th Edition Lite (ASI-Lite)** will be used to assess the severity of alcohol and any drug dependence and associated psychosocial impairment. This instrument is a modified version of the ASI [140].

**The Brief Symptom Inventory (BSI)** is a multidimensional symptom inventory designed to reflect psychological symptom patterns of psychiatric and medical patients.

**The Short Inventory of Problems (SIP)** is an assessment that measures physical, social, intrapersonal, impulsive, and interpersonal consequences of alcohol and drug consumption.

**The Brief Pain Inventory** is an assessment to measure pain symptoms.

**The Treatment Services Review (TSR)** is a brief, structured interview administered to collect information on the type and amount of services received by the patient outside of the study.

**Urine toxicology testing** will be performed at baseline to assess for THC, opioids, cocaine, and benzodiazepines. We will conduct rapid urine toxicology testing for opioids prior to each monthly VIVITROL injection.

**SF-12:** We will be collecting data on health and well-being using the SF-12 form.

**Substance Use Survey:** We will collect data on ongoing or new substance use, including cigarette use, using the Substance Use Survey.

**Patient Satisfaction:** A semi-structured interview, administered by a research assistant, will be used to assess overall satisfaction with the clinic setting, including specific components of treatment such as medication, nursing interactions, and physician visits.

**Opioid receptor genotyping:** A number of recent studies have identified specific genetic variants that predict responsiveness to naltrexone. In particular, a single nucleotide polymorphism in exon 1 (Asn40Asp) in the mu-opioid receptor gene (OPRM1) has been identified in numerous retrospective studies as highly correlated with clinical response (144-146). Subjects with one or two Asp40 alleles have a 74-87% response to naltrexone, as compared with a 49% response in those lacking this variant (146). In order to control for this important variable, and to further explore the interaction of this polymorphism with clinical response, we will perform targeted gene testing to identify the presence of the Asp40 allelic variant.

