#### ***End-of-treatment assessments***

The end-of-treatment assessments will include: Pharmacy fill/refill data, HAART medication adherence measures, HAART pill counts, TLFB for heavy drinking, OCDS, PEth, HIV drug resistance testing, HIV biological markers (CD4 lymphocyte count and HIV RNA levels), liver enzymes, platelet counts, hemoglobin, creatinine, sexual risk behavior assessment, SAFTEE, BAC, ASI, BSI, SIP, Brief Pain Inventory, TSR, SF-12, the Substance Use Survey, and patient satisfaction.

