**Table 1: Summary of Study Assessments**

	Wk -1	Wk 0	Wk 2	Wk4	Wk 6	Wk 8	Wk 12	Wk 16	Wk 20	Wk 24	Mn 9	Mn 12
History (demographic and clinical data) and physical exam	X											
Chart review for historical genotypic information	X											
SCID	X											
AUDIT	X											
OPRM1 genotyping	X											
Hepatitis B and C serologies	X											
Urine pregnancy test	X			X		X	X	X	X			
Liver enzymes (AST, ALT, GGT)	X			X		X	X	X	X	X	X	X
CBC, chemistries	X			X		X	X	X	X	X	X	X
CD4 count and HIV RNA	X			X		X	X	X	X	X	X	X
Standard HIV drug resistance testing and ultra-deep sequencing	X			X		X	X	X	X	X	X	X
Pharmacy fill/refill data for HAART adherence	X						X			X	X	X
Urine Drug Screen (for THC, opioids, coke, benzos at baseline; for opioids at other timepoints prior to VIVITROL injection)		X		X		X	X	X	X			
ACTG HAART medication adherence		X	X	X	X	X	X	X	X	X	X	X
HAART Persistence Questions		X	X	X	X	X	X	X	X	X	X	X
Visual Analog Scale (10cm): Adherence		X	X	X	X	X	X	X	X	X	X	X
Morisky 4-item Adherence Scale		X	X	X	X	X	X	X	X	X	X	X
Time-Line Follow Back (TLFB) for alcohol consumption	X		X	X	X	X	X	X	X	X	X	X
Alcohol Craving analog scale		X		X		X	X	X	X	X	X	X
OCDS		X		X		X	X	X	X	X	X	X
Substance Use Survey		X		X		X	X	X	X	X	X	X
PEth testing		X				X			X			X
Breathalyzer test (BAC)		X	X	X	X	X	X	X	X	X		
Sexual risk behaviors		X		X		X	X	X	X	X	X	X
SF-12		X		X		X	X	X	X	X	X	X
TSR				X		X	X	X	X	X	X	X
ASI-Lite		X								X		X
BSI		X								X		X
SIP		X								X		X
Brief Pain Inventory (+ Supplement)		X								X		X
SAFTEE		X	X	X	X	X	X	X	X	X		
VIVITROL injection		X		X		X	X	X	X			
Counseling Session		X	X	X	X	X	X	X	X			
Assessment compensation	X			X		X	X	X	X	X	X	X
Patient satisfaction survey						X			X			

4. **Statistical Considerations:** Describe the statistical analyses that support the study design.

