As the safety of VIVITROL has not been established in pregnant and nursing women, they will be excluded from participation. Women of child-bearing capacity must agree to use a reliable form of birth control. A urine pregnancy test will be performed at baseline and monthly. Pregnant women will be referred for other alcohol treatment. Women who become pregnant during the study will be taken off study medications immediately. Individuals with urine tests positive for recent opioid use, who are taking opioid medication for the treatment of pain, or have a diagnosis of current opioid dependence will be excluded. In case of an emergency situation requiring opioids, subjects will be provided with a card showing that they are receiving VIVITROL. This card will provide detailed information to medical personnel describing the special precautions necessary in the event that the subject should require pain management. Specifically, the amount of opioids necessary for analgesia may be greater than usual, and the resulting respiratory depression may be deeper and more prolonged. As a result, a rapidly acting analgesic that minimizes respiratory depression is preferred and the amount of the analgesic administration titrated to the needs of the patient in a setting equipped and staffed for cardiopulmonary resuscitation. In addition, this card will have a code number on it that can be used to identify which medication the subject is on. A phone number of the pharmacy and for the physician on call for the study will be listed on the card in the event of an emergency in which it is necessary to determine whether the subject is on active VIVITROL.

Rating scales and questionnaires The major risk of the assessments is the potential loss of confidentiality which is discussed in the section related to confidentiality below. To minimize any discomfort associated with reporting on sensitive behaviors, participants will be informed that they may refuse to answer questions that they are not comfortable answering. Questions related to eligibility determination and monitoring of safety and treatment response are not optional. If a person declines to answer these questions, we will advise them that they will not be able to participate and we will make a referral to other treatment if they are interested.

APPROVED BY THE YALE UNIVERSITY IRB 10/11/2018 VALID THROUGH 10/13/2019  

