**Baseline Assessments:**

Prior to entrance into the study each patient will undergo a medical history, physical and laboratory assessments [Complete blood count (CBC), chemistry panel, and viral hepatitis serologies]. A urine pregnancy test will be performed on female subjects and must be negative prior to beginning the study medication and will be checked monthly. Demographic data to be collected include age, gender, marital status, highest level education completed, employment, substance use history, duration of HIV disease, and a detailed HAART medication history. Charts will be extracted to collect information including medical co-morbidities, prior CD4 lymphocyte cell counts and HIV RNA levels, HAART medication history, and historical genotypic information from prior HIV drug resistance testing

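### The text requires monthly pregnancy testing, but Table 1 stops it at week 20, so the last depot interval (weeks 20–24) is never tested

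*Combined protocol and SAP*

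**What the plan says.** Three places in the text set the frequency of pregnancy testing, and they agree.

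- Section V.3, Baseline and in-treatment assessments: "A urine pregnancy test will be performed at baseline and each month thereafter and must be negative throughout the study".
- Section IX.2, Minimizing Risks: "A urine pregnancy test will be performed at baseline and monthly". The exclusion of pregnant and nursing women is explained there: "As the safety of VIVITROL has not been established in pregnant and nursing women".
- Section IX.4, Baseline Assessments: the test "must be negative prior to beginning the study medication and will be checked monthly".

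Table 1 has a row headed "Urine pregnancy test", marked at weeks −1, 4, 8, 12, 16 and 20. The cells for week 24, Month 9 and Month 12 are empty. The End-of-treatment assessments paragraph ("The end-of-treatment assessments will include: Pharmacy fill/refill data, HAART medication adherence measures" and so on) does not list the test, and neither does the follow-up paragraph.

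Injections are given every 4 weeks, at weeks 0, 4, 8, 12, 16 and 20 in Table 1. The Study Period paragraph sets the study period at 24 weeks.

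**The concern.** Sites work from the visit table. Followed as printed, it leaves out a test that the risk-minimization section promises. A woman who conceives during the 4 weeks after her last depot injection, or whose pregnancy becomes detectable only then, has no scheduled test at week 24 or at any later visit.

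By the plan's own statement, safety in pregnancy has not been established. Its adverse event definitions also class a birth defect after any dose as a serious adverse event. At stake are recognition of an exposed pregnancy, referral and safety reporting. No dosing decision is involved, because no injection follows week 20.

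**Working it through.** The plan gives no figure to reproduce here. The check is a cell-by-cell reading of Table 1 against the text. Every row read below has all 12 visit cells, so the blank at week 24 does not look like an extraction fault.

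**Step 1. Rows of Table 1**

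| Row | Visits marked |
|---|---|
| Injection | Wk 0, 4, 8, 12, 16, 20 |
| Opioid urine screen | Wk 0, 4, 8, 12, 16, 20 |
| Pregnancy test | Wk −1, 4, 8, 12, 16, 20 |
| Liver enzymes; CBC and chemistries; CD4 and HIV RNA | Wk −1, 4, 8, 12, 16, 20, 24, Mn 9, Mn 12 |
| Assessment compensation | Wk −1, 4, 8, 12, 16, 20, 24, Mn 9, Mn 12 |

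**Step 2. What monthly means in this plan.** Section X.2 (Payments for Participation) pays for six monthly assessments and lists baseline, Month 9 and Month 12 separately. Taking those three out of the compensation row leaves weeks 4, 8, 12, 16, 20 and 24, which is six visits. Week 24 is therefore one of the plan's monthly visits, and the pregnancy test is marked at five of the six. Other tests described as monthly follow the full pattern. CD4 count and HIV RNA, for example, "will be checked at baseline and monthly" and are marked at week 24.

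**Step 3. Whether weeks 20–24 count as treatment.** The Treatment section gives medication over a 24-week period at 4-week intervals. Section VI.5 puts the longest time on placebo at 24 weeks although the last injection is at week 20. The plan itself therefore counts the last interval as exposure.

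**Step 4. Coverage.** Six doses create six 4-week intervals: 0–4, 4–8, 8–12, 12–16, 16–20 and 20–24. The first five end with a test and the sixth does not.

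- Now: 5 of 6 intervals closed; uncovered 4/24 = 17% of treatment weeks.
- With a week 24 test: 6 of 6 intervals closed.

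**Step 5. Allowing for a detection lag.** A urine test may miss recent conceptions. Let L be the lag in weeks. This is an assumption, since the documents give no value. A test at week T detects conceptions up to week T − L. With the last test at week 20, the uncovered span is 24 − (20 − L) = 4 + L weeks. With the last test at week 24, it is 24 − (24 − L) = L weeks.

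| L (weeks) | Uncovered now | Uncovered with week 24 test | Gain |
|---|---|---|---|
| 0 | 4/24 = 17% | 0/24 = 0% | 4 weeks |
| 1 | 5/24 = 21% | 1/24 = 4% | 4 weeks |
| 2 | 6/24 = 25% | 2/24 = 8% | 4 weeks |

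The gain is 4 weeks whatever lag in this range is assumed.

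**The case against.** The strongest reply is that the pregnancy test is a pre-dose check. After baseline its row matches the opioid screen visit for visit. The plan also uses the word monthly for the injections themselves. The sentence requiring the test stands under in-treatment assessments, while week 24 has its own end-of-treatment list, which agrees with Table 1 in leaving the test out. The laboratory tests that continue to week 24 are study outcomes, so a safety check need not share their schedule.

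This reading fits the table but not the text. Where the plan ties a test to dosing, it says so: "We will conduct rapid urine toxicology testing for opioids prior to each monthly VIVITROL injection". None of the three statements on pregnancy testing says this, and one requires a negative result for the whole study. The comparison with outcome tests is indeed the weaker argument, but the count of six monthly assessments does not depend on it.

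Several other points stand and limit the concern:

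- Every injection from week 4 on has a test at the same visit, and week 0 is covered by week −1. No pre-dose check is missing.
- Effective birth control is required. The embryo effect cited was in the rat and rabbit at about 140 times the human dose.
- The percentages are shares of calendar time, not risk, and only half the participants receive active drug. As an illustration, if the Yale clinic's 40% women applied to its 50 participants, that would be 50 × 0.40 = 20 women, about 10 of them on active drug.
- Participants are still seen at week 24, Month 9 and Month 12, and adverse events in follow-up must be reported. A pregnancy could come to light that way, but this is incidental contact and not a scheduled test.
- The plan describes no follow-up of pregnancy outcome, and a term birth after a conception in weeks 20–24 would fall beyond Month 12. A week 24 test alone would not capture a birth defect.

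**Conclusion.** The concern holds. The text requires monthly testing throughout the study, and Table 1 and the end-of-treatment list leave the last of six dose intervals untested: 4 of 24 weeks (17%), or up to 6 of 24 (25%) if a 2-week detection lag is assumed. The consequence is a small gap in safety surveillance. It affects no endpoint, power calculation, blinding or dosing decision. The documents give neither the number of women of childbearing potential across the three clinics nor a pregnancy rate, so no expected number of missed pregnancies can be stated. The mismatch should be corrected because the plan promises the safeguard and the correction is very cheap.

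**What to change.** Mark the urine pregnancy test at week 24 in Table 1 and add it to the End-of-treatment assessments list. This costs one table cell, one list item and one urine test per woman of childbearing potential at a visit that already takes place. Conceptions shortly before week 24 may still be missed.

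If the investigators intend testing only before each injection, the three statements in Sections V.3, IX.2 and IX.4 must say so and state that the last dose interval is not tested. That would make the documents consistent but leave the gap open, so rewording alone is not an adequate substitute for the week 24 test.
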